**Table 1: Schedule of study visits**

Visit number	Screening		Pre V1	Treatment							Follow up				Optional	
	-2	-1		1	1b	1C	2	3	3b	3C	4	Pre V5	5	6	7	any time post dosing
Weeks	These visits can be combined. Treatment must start within 3 months of screening commencing 		A minimum of 72 hours prior to visit 1	0	1 day post visit1	3 to 5 days post visit 1	4	8	1 day post visit3	3 to 5 days post visit 3	9	A minimum of 72 hours prior to visit 5	14	20	52	
Days				0			28	56			63 (or one week post final injection)		98	140 (85 days post final dose)	366 (311 days post. final dose +/- 14 days)	
Informed consent	X															
Study drug administration				X			X	X								
Follow up telephone call 24 hours post IMP				X			X	X								
Physical Exam & ECG	X			X			X	X					X		X	
 Serum for AABs and immune markers				X							X		X		X	
DRB1*0401 genotype	X															
MMTT				X									X		X	
Photographs at injection site				X			X	X			X		X	X	X	
Blood sample to accompany skin studies (optional)								X								
Stitch removal from biopsy site (optional)										X						
urine or random serum c-peptide post meal		X		X									X		X	
72 hour continuous glucose monitoring			Attach CGM	X								Attach CGM	X		X	
Serum for Cystatin C				X							X		X	X	X	
Urinalysis for blood, protein, and beta-2 microglobulin		X		X			X				X		X	X	X	
Serum and urine (morning) sample to measure gold concentrations				X pre dose	X 				X 		X		X	X	X	
T cell (immune biomarker) assays (blood)				X				-			X		X		X	
 LN aspiration 0/3-5d				X		X		X		X						
 Safety blood samples		X		X			X				X		X	X	X	
HbA1c measurement		X		X			X				X		X		X	
Vital signs	X	X		X			X	X			X		X	X	X	
Adverse Event assessment/con meds		X	X	X	X	X	X	X	X	X	X	X	X	X	X	
Urine pregnancy test		X		X			X	X					X	X		
Record of insulin use	X			X			X	X					X		X	
 Blood glucose profile/insulin usage				X			X	X					X	X	X	

Assessment of glycaemic control/review blood sugar recordings				X				X	X					X		X	
Skin biopsy (optional) 																	X
Contact hypersensitivity testing (optional) 																	X
Suction blister (optional) 																	X
XHFS survey				X										X			
ADDQoL				X										X		X	
DTSQs				X										X		X	
DTSQc														X			

Screening can be up to 3 months

Treatment visits 1, 2 and 3 should be every 28 days +/- 3 days and follow up visit 5 should be at 14 weeks +/- 1 week

If dosing is delayed beyond 3 months, all test other than genotype should be repeated.

Samples to be taken post dose.

[figure not shown]
Details supplied in outcome assessment section 6 and safety assessment section 10.

Contact hypersensitivity testing will be done once post dose. It involves 3 visits (the 2nd visit can be done at home).

 These tests will be done in subjects with a persistent reaction (optionally, post-dose).

Figure 1. Flow chart of ascertainment, recruitment and screening through to IMP administration.

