### **4.4 Secondary endpoints**

- T cell responses to C19-A3 GNP as determined by changes from baseline of interferon gamma and IL-10 ELISPOT responses to this peptide in blood following treatment at weeks 0, 9 and 14.
- T cell responses to C19-A3 GNP as determined by changes from baseline of interferon gamma and IL-10 ELISPOT responses to this peptide in draining axillary lymph node before treatment and following the last treatment administration.
- Changes in additional immunological biomarkers (e.g. flow cytometry profiles, T reg assays, autoantibodies, beta cell and T cell free DNA markers) from baseline at week 0, 9 and 14.

- Effects on residual insulin requirement and c-peptide secretion at week 14 as compared to baseline as assessed by a mixed meal tolerance test and a stimulated urine c-peptide test.
- Effects on glycaemic control assessed by blood sugar profiles and HbA1c at week 14 as compared to baseline
- Questionnaires on quality of life and diabetes self-management.

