### **6.17 Specimen handling**

Samples for local laboratory assessment may be taken at a time convenient for same day processing by the local laboratory. Samples for immunologic or metabolic studies, HLA typing or autoantibodies will be drawn before 12.00 and sent by approved courier to the appropriate laboratory or stored locally for later analysis. At dosing visits blood draw will take place prior to administration of the IMP.

[figure not shown]

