**Figure 3 Blood draw schedule:**

	Screening		Treatment					Follow-up				
Visit no:	-2	-1	1	1b	2	3	3b	4	5	6	7	post
Weeks			0		4	8		9	14	20	52	final
Days			0	1	28	56	57	63	98	140	366	dose
Safety blood samples HbA1c & glucose		11			11			11	11	11	11	
DRB1*0401 and A*02	2											
Serum for Aabs	2											
Serum for insulin cell free DNA	8											
Serum for: Aabs, cystatin-c, insulin cell free DNA, other			10					10	10	10	10	
MMTT			25						25			
Blood to accompany skin biopsies												20
Serum for gold concentrations (morning urine also to be sent)			1	1			1	1	1	1	1	
PBMC's T reg assay, T cells, CD4 & CD8 tetramers, Elispots & biobank storage.			64					64	64*		64	
Flow cytometry			2					2	2		2	
Serum for gold concentration before contact hypersensitivity testing												1
Total	12	11	102	1	11	20	1	88	113	22	113	1

\*in subjects with immune responses of interest visit 4, an additional blood sample up to 70mls (35mls for under 18s) may be requested between visit 4 and visit 6.

Volumes for the study within an 8-week period coincide with guidelines of the National Institute of Health (ie blood collection should be <550ml per 8-week period for adults, and no more than 5ml/kg in a single day and no more than 9.5ml/kg in any 8 week period for under 18's) and are those used by the Type 1 diabetes clinical trial consortium, Type 1 Diabetes Trial Net ([www.diabetestrialnet.org](http://www.diabetestrialnet.org)).

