The procedures are as follows. Start IV line. Obtain baseline blood samples at 0 minutes, and any other test samples required at that visit (e.g. HbA1c, T cell studies, PBMCs islet cell autoantibodies). For each time point blood samples are 1.2 ml fluoride tube for glucose and 1.2 ml serum tube for C-peptide. In addition, for each test the first sample (0 minutes) and the last sample (120 minute for MMTT) will be used to obtain a meter ketone reading, which is recorded. A first blood sample is drawn immediately before the participant starts drinking the liquid meal (formal "baseline samples"). The patient is given the standardized liquid meal: Ensure Plus 6 ml/kg (Maximum 360ml) to be ingested within 5 minutes. Blood samples are drawn at times: 15, 30, 60, 90 and 120 minutes, after the end of ingestion of Ensure Plus (note: time runs from the start of ingestion). After the test is completed, the participant eats and receives insulin as appropriate and prescribed by the local investigator. A urine sample at the 120 minute time point will also be collected for c-peptide creatinine ratio as an alternative marker of insulin production.

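### Table 1 footnote 2 marks the week-0 autoantibody and immune-marker serum as post-dose, against the pre-dose rule in Protocol 6.17

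*Protocol*

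**What the plan says.** Protocol Table 1 has a row "Serum for AABs and immune markers" whose label carries superscript 2, with samples at visits 1, 4, 5 and 7. Footnote 2 reads "Samples to be taken post dose". Visit 1 is week 0 and the first injection.

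Protocol 6.17 gives a general rule: "At dosing visits blood draw will take place prior to administration of the IMP". In the meal-test procedure, Protocol 6.18.1 takes with the 0-minute sample "any other test samples required at that visit (e.g. HbA1c, T cell studies, PBMCs islet cell autoantibodies").

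Figure 3 gives one 10 ml entry at visit 1 for "Serum for: Aabs, cystatin-c, insulin cell free DNA, other".

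The week-0 serum is the reference for two sets of changes:
- SAP 5.1.1 takes the week 0 to week 14 difference in islet autoantibodies as part of the primary safety outcome (accelerated beta-cell loss).
- Protocol 4.4 and SAP 5.1.2 take changes from baseline in further biomarkers, including cell-free DNA from beta cells and T cells.

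For a different assay, blood ELISPOT, Protocol 4.4 and SAP 5.1.2 speak of change from baseline in responses "in blood following treatment at weeks 0, 9 and 14".

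**The concern.** A change from baseline needs a baseline taken before treatment. Read literally, the visit table tells staff to draw this serum after the first injection, while the specimen-handling section tells them to draw all blood beforehand. The visit table is what a site is likely to work from on the day. A post-dose week-0 sample cannot be redrawn. With 8 subjects at two centres, there is little room to absorb a difference in practice between sites. The ELISPOT wording raises a similar question for another assay, because it lists the baseline week among the times after treatment.

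**Working it through.** No power or sample-size figure is involved. The check is a comparison of passages and two sums.

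**1. Where footnote 2 changes what staff do**

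| Place in Table 1 with superscript 2 | Timing | Effect of the footnote |
|---|---|---|
| Gold samples, visits 1b and 3b | Day after a dose | None; already post-dose |
| Autoantibody and immune-marker serum, visits 4, 5, 7 | After the last dose | None; already post-dose |
| Autoantibody and immune-marker serum, visit 1 | Day of first dose | Moves the draw to after the injection |

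Only the visit-1 serum cell is affected. The row "Serum and urine (morning) sample to measure gold concentrations" is explicitly marked pre-dose at visit 1. The same table therefore shows one sample labelled pre-dose and another labelled post-dose at the same visit.

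**2. Against the text.** Section 6.17 puts blood at dosing visits before the drug. Section 6.18.1 draws autoantibody samples at meal-test minute 0 and does not itself state the order of test and injection. Because the meal-test samples are blood draws at a dosing visit, 6.17 puts them before the injection too. Both sections conflict with footnote 2 at visit 1.

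**3. Is there a second tube?** Figure 3, visit 1: 10 (serum) + 25 (meal test) + 1 (gold) + 64 (cells) + 2 (flow cytometry) = 102 ml, which equals the printed total. A second 10 ml serum draw would make 112 ml. The plan therefore has a single serum draw, and a site following the footnote would have no pre-dose week-0 serum for this row.

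**4. Is there another pre-treatment sample?** Figure 3, visit -2: 2 (HLA typing) + 2 (autoantibodies) + 8 (insulin cell-free DNA) = 12 ml, which equals the printed total. Table 1 shows no screening sample on this row, but the SAP's data-file Table 3 lists both analytes at baseline and its Table 6 has a visit -2 column. A screening value should therefore exist for both. It is imperfect because it can be up to three months old, the analysis names week 0 as the reference, and Figure 3 lists no screening draw for the remaining immune markers.

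**5. Does the SAP settle it?** In the SAP's visit table this row has an asterisk, as do lymph-node aspiration, safety bloods and the glucose profile. In the Protocol those three rows carry superscript 3, the cross-reference to sections 6 and 10. This suggests that 3 was meant. The asterisk also marks the gold cells at 1b and 3b, and the SAP text supplied does not define it, so the evidence is supportive but not decisive. SAP 5.1.1 does not say whether week 0 is before or after the dose.

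**6. Size of bias.** If the post-dose value is (1 + x) times the pre-dose value, a patient who has not changed shows a relative change of 1/(1 + x) − 1. The documents give neither the size nor the sign of x for any analyte, so no figure follows.

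**7. ELISPOT wording.** The Table 1 row for T cell assays in blood has no footnote 2, and 6.17 governs it. The endpoint is itself a change from baseline, and the autoantibody and cell-free DNA bullet lacks the post-treatment phrase. This is a separate looseness and does not corroborate the footnote.

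**The case against.** The best reply is that the Protocol already states the order. Section 6.17 is explicit and general, 6.18.1 agrees with it, and the superscript looks like a slip for 3 or a conversion error. Screening serum exists. Autoantibody levels are unlikely to move within hours, so the part of the primary outcome that uses them is little exposed. The analysis is descriptive, unpowered, and plans no comparison between sites.

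Most of this stands, and it is why the point is minor. It does not remove the contradiction: as printed, the visit table gives the opposite instruction for the one sample where order matters.

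The documents do not support several stronger readings that a reader might infer:
- *The only pre-treatment value is lost.* Only the pre-dose week-0 value is at risk; Figure 3 has screening serum for autoantibodies and insulin cell-free DNA.
- *The cystatin-C baseline is post-dose as well.* Cystatin-C shares the 10 ml draw in Figure 3, but it has its own Table 1 row without footnote 2. The shared draw points as much to pre-dose as to post-dose.
- *The ELISPOT baseline is drawn after treatment.* The phrase is loose endpoint wording, not a sampling instruction.
- *All 8 baselines are biased by some percentage.* That would need both sites to disregard 6.17 and a same-day shift for which the documents give no data.

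**Conclusion.** As printed, footnote 2 on this row contradicts 6.17 and 6.18.1 at visit 1. Pre-dose sampling is the likelier intent. If the footnote were followed, the pre-dose week-0 serum for the autoantibody and cell-free DNA changes would be missing, with screening serum as a partial substitute. The practical exposure is mainly cell-free DNA. How many subjects are affected depends on what the sites did, which the documents do not show. The conclusion assumes that the superscript in the issued PDF is a 2 and that autoantibodies are stable over hours; the second is a judgement that the documents neither support nor contradict. Severity: minor, an inconsistency to correct rather than a flaw in the design.

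**What to change.** 1. In Protocol Table 1, reconcile the row with 6.17: change its superscript from 2 to 3 and mark the visit-1 cell as pre-dose, as the gold row already does.
2. In Protocol 4.4 and SAP 5.1.2, reword the blood ELISPOT times to: at week 0 (before the first dose), week 9 and week 14.
3. Compare recorded draw times with injection times at visit 1 and flag any serum drawn after dosing.
4. Do not discard flagged baselines outright; with 8 subjects that would throw away autoantibody values that are probably sound. For cell-free DNA, repeat the summary without the flagged baselines or with the screening value in their place, and report it beside the main summary.

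The cost is one superscript, one table cell, one phrase in each document, a check of draw times and a little extra analysis. No new sample is needed.

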### Recruiting clinical sites

## **5 TRIAL MEDICATION**

### **5.1 IMP**

The IMP will be delivered as sterilised solution in small vials produced by Baccinex SA (Courroux, CH), and stored, QP released and shipped to the clinical sites by PharmaKorell GmbH (Lörrach, Germany).

The vials should be stored refrigerated at 2-8 °C.

The IMP will be 10ug of C19-A3 peptide Gold NPs injected by Nanopass microneedles, delivered intradermally into the upper arm, in 50ul volume.

### **5.2 Dosing regimen**

C19-A3 GNP will be administered intradermally via CE marked Nanopass 600nm microneedles. 3 doses will be given at 4 weekly intervals. The dose given will be equivalent to 10ug of C19-A3 peptide. Thus the cumulative dose will be 30ug.

### **5.3 Drug accountability**

The will arrange transfer of IMP to local IMP Storage and Supply Sites. The local Site Pharmacy will then take responsibility for IMP accountability by ensuring that: the IMP is stored in a secure location, segregated from other medicines; used and returned medication is kept separate from unused medication; storage conditions are monitored and recorded; IMP is dispensed to participants in accordance with the trial protocol; unused medication is returned to the study team or disposed of as authorised by the study team. Full accountability records will be kept for all aspects of IMP handling. IMP accountability records will be monitored by the Sponsor.

[figure not shown]
### **5.4 Subject compliance**

Patients will be allowed 28 days +/- 3 days between treatments, but every effort should be made to dose every 28 days. Where a visit is > 3 days late it should be documented as a protocol violation and scheduled as soon as possible, with subsequent dosing visits recommenced on a 28 day schedule after this. Where the interval between 2 doses is > 42 days, the dose will be considered to have been missed and the subsequent dose should be given. Subject attendance and compliance will be recorded. If a treatment is missed the subject will continue in follow-up but an additional subject will be recruited, so that a total of 8 subjects will receive all 3 doses.

Patients will be allowed to attend for follow up visit 4 (week 9 or one week post final injection) +/- 1 day of schedule, visit 5 (week 14), +/- 1 week of visit schedule and visit 6 (week 20) must be a minimum of 85 days post final dose/+2 weeks. There will also be an optional visit 7 (week 52) at a minimum of 311 days post final dose +/- 2 weeks. There will be an optional skin blister, an optional skin biopsy and an optional contact hypersensitivity testing performed anytime post-dose (referring to post final dose). Any visits outside of this guidance will be considered a protocol deviation.

**Figure 2** Chart indicating dosing schedule

### 5.5 Dosing strategy:

This is an open label uncontrolled early phase safety study, so no blinding or randomisation will be performed. In keeping with standard phase 1 study designs, no placebo or control group is included as the primary aim is to establish whether there are any major unexpected safety issues in the use of this IMP for the first time in man.

### 5.6 Concomitant medication

Patients will be supported to receive optimal care during the study, to include daily insulin injections. Routine vaccinations (flu and others) should be avoided for the duration of the study unless clinically essential (eg during periods of high risk flu exposure). Use of  $\beta$ -cell stimulants (e.g. sulphonylureas), glucagon-like peptide-1 agonists, dipeptidyl peptidase-IV inhibitors, insulin sensitisers (e.g. metformin, thiazolidinediones) that may affect insulin production, and the use of immunosuppressive or immunomodulatory therapies (including systemic but not topical or inhaled steroids) which may modulate immune responses is not permitted. Use of other drugs with potential effects on the immune system, insulin sensitivity or  $\beta$ -cell function, where these are considered clinically essential for treatment of concomitant medical conditions, will be discussed with the Chief Investigator. See also 6.3

## 5.7 Concomitant health issues

Study drug should not be administered if a subject has had a febrile illness within the last 3 days as this may activate T cells non-specifically. Under these circumstances, the missed study visit should be delayed to the earliest next feasible date (but no longer than 14 days) and the study continued.

Females will be advised not to become pregnant within 85 days following the date of their final treatment of IMP and will be advised to continue using adequate contraception until this time point See section 6.2

Males will be advised not to father a child within 85 days following the date of their final treatment of IMP.

## 5.8 Measures to avoid bias

The study will be open label. Assessment of immune responses will be conducted blinded from metabolic parameters in the first instance. All samples will be labelled with a study ID only, and laboratory staff will know whether samples are from the same subject but not the identity of the subjects.

## 5.9 Timescales

**5.9.1 Proposed Trial Start:** July 2016

**5.9.2 Projected Trial Completion (amended):** January 2019

**5.9.3 Trial Duration:** 26 months

**5.9.4 Duration of Each Patient's Participation:** 12 months (52 weeks excluding screening), the last visit (visit 7) is optional and if the participants choose not to take it the duration would be 5 months (20 weeks excluding screening), there will be three optional tests performed post final dose

## 6 SELECTION AND WITHDRAWAL OF SUBJECTS

### 6.1 Study population

8 subjects with a diagnosis of Type 1 diabetes will be included in the study. Autoimmune diabetes will be confirmed by measurement of islet cell autoantibodies. Patients will be required to possess the HLA-DR4 (*B1\*0401*) genotype.

### 6.2 Inclusion criteria

1. Clinical diagnosis of type 1 diabetes for > 3 months (dated from the first insulin injection).
2. Commenced on insulin treatment within 1 month of diagnosis.
3. Age 16 to 40 years

4. 2 hour post-meal UCPCR > 0.2 nmol/mmol or random serum sample > 60 pmol/l on at least one occasion (maximum 3 tests on different days)
5. Possession of 0401 allele at the *HLA-DRB1* gene locus
6. The following birth control methods should be used (considered highly effective with a failure rate of less than 1% per year when used consistently and correctly):
  - combined (estrogen and progestogen containing) hormonal contraception associated with inhibition of ovulation:
    - oral
    - intravaginal
    - transdermal
  - progestogen-only hormonal contraception associated with inhibition of ovulation:
    - oral
    - injectable
    - implantable
  - \_intrauterine device (IUD)
  - \_intrauterine hormone-releasing system ( IUS)
  - \_bilateral tubal occlusion
  - \_vasectomised partner (provided that the partner is the sole sexual partner of the trial participant and that medical assessment of azoospermia has been confirmed)
  - Sexual abstinence (defined as refraining from heterosexual intercourse during the duration of the trial)
7. Written and witnessed informed consent to participate.

### 6.3 Exclusion criteria

1. HbA1c > 86mmol/L (10%).
2. Females who are pregnant, breast-feeding or not using adequate forms of contraception.
3. Previous diagnosis of renal disease including glomerulonephritis or nephropathy.
4. Raised serum creatinine or abnormal urine albumin/creatinine ratio (ACR) (values above the laboratory reference range). If the initial ACR is raised, this should be repeated on two further occasions as first morning samples. The subject can be included if both of these samples are negative (within the reference range).
5. Use of immunosuppressive or immunomodulatory therapies, including systemic steroids within 1 month prior to receiving the IMP and any monoclonal antibody therapy given for any indication. Note that previous exposure to proinsulin peptide C19-A3 in a clinical trial is an exclusion criterion.
6. Use of cannabis within one month prior to trial entry.
7. Use of any hypoglycaemia agents other than insulin, for more than 6 weeks, at any time prior to trial entry.
8. Use of inhaled insulin.
9. Known alcohol abuse, drug abuse, HIV or hepatitis.

10. Allergies to drug components or any excipients.
11. Any other medical condition which, in the opinion of investigators, could affect the safety of the subject's participation or outcomes of the study, including immunocompromised states and autoimmune conditions.
12. Subjects should not have had immunisations (flu and others) for 1 month prior to trial entry and should not receive any during their time in the trial – see section 5.6.
13. Recent subject's involvement in other research studies which, in the opinion of investigators, may adversely affect the safety of the subjects or the results of the study.
14. Abnormal ECG findings.

